**NCT Number 02473471**

**February 21, 2017**

## **MATERIAL AND METHODS:**

### **Trial design and any changes after trial**

#### **Commencement**

This study was a split mouth randomized clinical trial with a 1:1 allocation. Methods were not changed after trial initiation.

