### **Sample size calculation**

The sample size was calculated based on a type I error frequency of 5%. According to the power analysis and assuming a large effect size difference between groups (effect size= 0.8), the power analysis yielded 28 subjects per group at a conventional alpha level ( $p = 0.05$ ) and desired power ( $1 - \beta$ ) of 0.90, yielding a total sample size estimate of 56 subjects. All calculations were performed with the computer application G-Power .

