## **Randomization (random number generation, allocation concealment, implementation)**

The intervention was randomly allocated to either right or left side with 1:1 allocation ratio. The randomization was accomplished using the permuted random block size of 2 with random generation function in Excel (Microsoft, Washington). Subsequently, the random sequence to either right or left were concealed in opaque envelopes and shuffled before the intervention to increase the unpredictability of the random allocation sequence. Each patient was asked to pick one sealed envelope to assign to the surgical intervention either on the right or the left side. Allocation concealment was aimed to prevent selection bias and protect the assignment sequence until allocation.

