### **Outcomes (primary and secondary) and any changes after trial commencement**

#### **Primary Outcomes**

**The** rate of tooth movement as primary outcome was determined by indirect measurement of study models and direct intraoral measurement as the following:

Alginate impressions were taken every month and study models were fabricated. The study models were then scanned with Ceramill Map 400- scanner with an accuracy of 0.02 mm (AmannGirrbach, Koblach, Austria) to obtain the three-dimensional (3D) model. By using Ceramill Mind design (CAD: computer-aided design) software (AmannGirrbach, Koblach, Austria), 3D model measurements were obtained. The baseline 3D digital model (M0) was superimposed to 3D digital models of following months (M1: 1st month, M2: 2nd month, M3: 3rd month) to determine the anteroposterior displacement of canines. The stable reference landmark used was the rugae area as recommended by other studies . To superimpose two

3D digital models, a generic visualization mesh of the following 3D model was added to the baseline model; and then performs registration of the selected reference points at rugae area (Figure 4-A,B). The best fit matching of the superimposition was evaluated by a color map with a spectrum of colors in which blue color represented the best matching while red represented the worst (Figure 4-C). From buccolingual view, the amount of canine's displacement was measured from the most middle projection from the distal surface of upper canines in baseline model to the most middle projection from the distal surface of upper canines of superimposed transparent models (M1, M2, M3) (Figure 5-A). A reference plane parallel to the bracket slots was used to ensure the standardized orientation of all measurements from buccal view (Figure 5-C). From the occlusal view, the same point was localized at the middle of the distal surface of canines to be parallel to the line of arch anterioposteriorly (Figure 5-B). Additionally, Direct measurement of distance between canine and second premolar in the patient's mouth was done every week using digital caliper (IOS, USA), from upper mesial wing of the canine bracket to upper distal wing of second premolar bracket in both right and left sides parallel to the occlusal plane for 3 months period.

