#### **Statistical analysis (primary and secondary outcomes, subgroup analyses)**

Statistical analysis was accomplished using the Statistical Package for the Social Sciences computer software (SPSS 20.0, SPSS Inc., IL, USA). Probability values equal or less than 0.05 were considered significant. Independent sample t-tests were calculated to analyze the results of the primary outcome and secondary outcomes to compare the difference between MOP and control sides. Similarly, independent sample t-test was performed to compare the amount of root resorption before and after three months in MOP and control sides separately. Chi-square was used for analysis of categorical data including the willingness to repeat the procedure and recommend it to a friend. Descriptive statistics were used to describe the satisfaction and ease of the procedure.

Reliability coefficient (Cronbach's Alpha) was used to evaluate the reliability of measurements of primary outcomes. One examiner did all measurements, and all subjects were randomly selected. Six of 3D superimposed digital models had been chosen randomly. Superimpositions on the rugae area and canine displacement were measured twice within 2-week interval. Reliability coefficient (Cronbach's Alpha) was 0.95, showing excellent superimpositions and measurement agreement.

For intraoral measurements, intra-examiner reliability was done in the lower arch after reaching 0.019x0.025 stainless steel arch wire and teeth were in a passive state; all cases were non-extraction in the lower arch. Six of subjects were selected randomly, and measurements were done twice with the 2-week interval. Measurements were done from the upper mesial wings of the lower canine bracket to the upper distal wing of the lower second premolar bracket. Reliability coefficient (Cronbach's Alpha) was 1.00, indicating excellent measurement agreement.

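### Paired split-mouth outcomes are analysed with independent-samples t-tests, so the standard errors and p-values for MOP versus control are wrong

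*Combined protocol and SAP*

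**What the plan says.** The trial design section states: "This study was a split mouth randomized clinical trial with a 1:1 allocation". The randomization section makes the side of the mouth the randomised unit: "The intervention was randomly allocated to either right or left side with 1:1 allocation ratio". Under Primary Outcomes, the caliper distance is recorded "in both right and left sides parallel to the occlusal plane for 3 months period", and canine displacement is taken from monthly 3D models of the same patients. Each patient therefore contributes a matched pair.

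The statistical analysis section then specifies, for the comparison of the MOP side with the control side: "Independent sample t-tests were calculated to analyze the results of the primary outcome and secondary outcomes". It uses the same test a second time, within each side: "independent sample t-test was performed to compare the amount of root resorption before and after three months in MOP and control sides separately". The threshold is given as "Probability values equal or less than 0.05 were considered significant", with no mention of sidedness.

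No paired test, mixed model or other allowance for within-patient correlation appears anywhere. The sample size section also reads as a two-group plan: 28 per group and 56 in total, for an effect size of 0.8 and power of 0.90.

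**The concern.** The independent-samples t-test assumes that the two sets of values come from unrelated people. Here they come from the same mouths, and share the patient's age, sex, bone biology and response to treatment. A split-mouth design is chosen so that this shared variation cancels in the within-patient difference. The planned test puts it back into the standard error.

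If the two sides are positively correlated, which is the usual reason for choosing the design, the test is too conservative. Its real type I error is below 5%, intervals built on it are too wide, and moderate effects on tooth movement can be missed. For root resorption and the periodontal and plaque indices the error runs in an unsafe direction, because an inflated standard error makes a difference in harm harder to detect.

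**Working it through.** **Inputs from the documents.** Randomised unit: side within patient (Randomization). Effect size 0.8, alpha 0.05, power 0.90, 28 per group, 56 in total (Sample size calculation). Test: independent-samples t-test (Statistical analysis).

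**Assumptions.** The documents give no SD and no rho. I assume rho from 0.3 to 0.8, and also look at rho = 0 and at a negative value. I take 28 as the number of patients and a two-sided 5% test.

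**Step 1: the plan's own figure.** For two independent groups with d = 0.8 and alpha 0.05, using the noncentral t distribution:
- One-sided: n = 28 per group, power 0.905. This matches.
- Two-sided: n = 34 per group; power at 28 per group is 0.836. This does not match.
- Paired, with 0.8 taken as the standardised within-patient difference: 15 patients (one-sided) or 19 (two-sided). Neither matches.

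Of these calculations, only the one-sided, two-independent-groups one gives 28. The unpaired assumption is therefore in the design calculation too, and is not just loose naming of a test.

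**Step 2: the standard error.** With a common SD sigma and n patients:
- Variance used by the independent test: 2·sigma²/n
- True variance of the mean difference: 2·sigma²·(1 − rho)/n
- Ratio of standard errors: 1/sqrt(1 − rho). For rho = 0.5 this is 1/sqrt(0.5) = 1.41. It does not depend on n.

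**Step 3: type I error and power.** Bivariate normal pairs were simulated with n = 28 and 100,000 replicates per cell. The pooled two-sample t-test (54 df) was compared with the paired t-test (27 df). Power is shown as unpaired vs paired.

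| rho | SE ratio | Type I error, unpaired | Power at 0.5 SD | Power at 0.8 SD |
|---|---|---|---|---|
| 0 | 1.00 | 5% | 45% vs 44% | 84% vs 82% |
| 0.3 | 1.20 | 2% | 44% vs 58% | 88% vs 93% |
| 0.5 | 1.41 | 0.7% | 43% vs 72% | 91% vs 98% |
| 0.7 | 1.83 | 0.08% | 42% vs 91% | 95% vs >99% |
| 0.8 | 2.24 | 0.01% | 41% vs 98% | 97% vs >99% |

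The paired test holds its 5% level at every rho. At rho = −0.2 the unpaired standard error is 0.91 times the correct one and its type I error is about 7%, so the direction reverses.

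**Step 4: 28 or 56 patients.** If the total of 56 means patients, the standard error ratios are the same. Type I error is about 2%, 0.6% and 0.06% at rho 0.3, 0.5 and 0.7. Power at 0.5 SD and rho = 0.5 is then about 82% vs 96%.

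**Step 5: root length before and after.** The same canine is measured twice, so the formula in Step 2 applies again. At an assumed rho of 0.9 between the two readings, the standard error is 1/sqrt(0.1) = 3.2 times too large.

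**The case against.** The strongest reply is that the error is mild or harmless for the main question. At the plan's own effect size of 0.8 SD, the unpaired test still has 88% to 97% power over the assumed range, and with positive correlation a significant primary result would stand. The large power gaps arise at 0.5 SD, an effect that the documents do not mention. The size of the error rests on an assumed rho: at 0.1 the type I error is still about 4%, and power at 0.8 SD is 85% vs 86%. The plan mentions no confidence intervals. Some outcomes are also outside the problem: willingness to repeat or recommend uses chi-square, satisfaction and ease are only described, and pain is described only after the MOP procedure.

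Much of this stands as a limit on scope. The finding applies to outcomes compared between MOP and control sides, the point about intervals is a consequence rather than planned text, and a large benefit would probably still be detected. None of it supports the test. Protection against false positives holds only if rho is not negative. A conservative test gives no reassurance about harms. The paired test is valid at any rho and gives up almost nothing if rho is zero.

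**Conclusion.** The concern holds. The planned test contradicts the design in each MOP-versus-control comparison, including the primary outcome, and again in the before-and-after root comparison. That conclusion needs no assumption. Its size does depend on rho, which is not given: for 0.3 to 0.8, standard errors are 20% to 124% too large and the nominal 5% test operates at about 2% down to 0.01%. The practical loss falls mainly on moderate effects and on null findings for harms. The power figures assume 28 patients, normal data and a two-sided test; the standard error ratio needs only equal variances on the two sides. Because the defect governs the primary p-value, it must be fixed before the results are relied on.

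**What to change.** - **Primary outcome and root resorption:** replace the independent-samples t-test with a paired t-test on the within-patient difference (MOP minus control), reported with its 95% confidence interval.
- **Repeated measures:** the paired test applies at one named time point. If the monthly models or weekly caliper readings are analysed together, use a mixed model with side, time and their interaction, and random effects for patient and for side within patient. A random-intercept model matches the paired t-test only for one complete pair per patient with non-negative correlation.
- **Periodontal and plaque indices:** use the Wilcoxon signed-rank test. Canines and second premolars are both scored, so first define one value per side.
- **Root length before and after, within each side:** use a paired test here as well.
- **Sample size text:** restate it in patients on a paired basis, giving sidedness and the assumed rho. For d = 0.8 between sides, 90% power and two-sided 0.05, the paired test needs 35, 25, 19 or 12 patients at rho 0, 0.3, 0.5 or 0.7.

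The cost is a change of wording in two sections and a re-run of existing data in the same software. No new data are needed. The only statistical price is about 1 point of power if the two sides are uncorrelated (82% vs 84% at 0.8 SD).

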## **Secondary Outcomes**

Root resorption was evaluated, as a secondary outcome, using the periapical radiographs of the canines before canine retraction and after three months. One operator, using parallax technique made all digital periapical radiographs by the same X-ray machine (RXDC eXTend, Myray, Italy), set up at 7 mA, 60 kV with an exposure time of 0.32 second. DIGORA Optime digital imaging plate system with its phosphor plate films (Soredex, Finland) was used in this study. Intraoral XCP film holders were used (Dentsply Rinn, Elgin, USA). Root resorption was measured using DIGORA for Windows 2.8 software, (Soredex, Finland). All radiographs were calibrated by 15.63 pixels per mm according to the manufacturing instruction. Root resorption in millimeter (mm) was measured by the difference between root length at baseline (R1) and after three months (R2). The reference point was the midpoint of mesial and distal cementoenamel junction (CEJ). The root length was calculated from root apex to the midpoint of cementoenamel junction (CEJ).

Periodontal index and plaque index were also evaluated clinically in both upper

canines and second premolars before canine retraction and after three months according to Löe. Both pain intensity and interference were evaluated using Visual Analog Scale (VAS) from 0 to 10 Numeric Rate Scale (0= no pain, 10= severe pain). The participants filled out a questionnaire to assess the pain intensity immediately, after 1 hour, 12 hours, day 1, day 3, day 5 and day 7 following MOP intervention. Pain interference with daily life was assessed after MOP intervention on 1, 3, 5 and 7 days in which patients were asked to provide their subjective answers of pain during eating, pain awakened them at night, the feeling of discomfort and swelling on the surgical side. Numeric Rate Scale was also used to rate the level of satisfaction (0= not satisfied, 10= very satisfied) and easiness of MOP procedure (0= very easy, 10= very complicated). Moreover, the patients were asked if they were willing to repeat the procedure and recommend to a friend using categorical data (Yes or No). There were no changes to the outcome measures after trial commencement.

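### Plaque and periodontal indices: the planned side comparison has no baseline term, ignores the split-mouth pairing, and does not name the value tested

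*Combined protocol and SAP*

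**What the plan says.** The trial design section states: "This study was a split mouth randomized clinical trial with a 1:1 allocation". Each patient therefore supplies one MOP side and one control side.

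Under Secondary Outcomes, the plan says "Periodontal index and plaque index were also evaluated clinically in both upper" "canines and second premolars before canine retraction and after three months according to" a published index system. So each index has two visits and two teeth per side.

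The Statistical analysis section names independent-samples t-tests to "analyze the results of the primary outcome and secondary outcomes to compare the difference between MOP and control sides". No paired test, covariate or mixed model is named for any outcome.

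Other outcomes are defined relative to a starting value. Root resorption is baseline minus three-month root length and has a before-after test within each side. Canine displacement is measured from the baseline model. The two indices have no such definition.

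**The concern.** Two features of the data that bear on precision have no stated role in the test. One is the pre-retraction score, which is already collected. The other is the matching of both sides within one mouth, which is the reason for a split-mouth design.

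With root resorption, these indices are the trial's main side-by-side measures of harm. A non-significant result is likely to be read as showing no periodontal harm from MOPs, so an imprecise comparison matters here. Leaving the analysed value open also lets the choice between three-month score and change be made after the data are seen.

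**Working it through.** **Inputs from the documents.** The Sample size calculation gives "The sample size was calculated based on a type I error frequency of 5" percent, "assuming a large effect size difference between groups (effect size= 0.8"), and "the power analysis yielded 28 subjects per group at a conventional alpha level", with power "of 0.90, yielding a total sample size estimate of 56 subjects".

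**The plan's own figure.** An independent-samples t-test with d = 0.8, alpha 0.05 and power 0.90 needs 28 per group one-sided (power 0.905), which matches. Two-sided it needs 34, and 28 gives 0.836. This point does not depend on that difference; I use only n = 28.

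**Assumptions, none of them in the documents.**
- 28 patients, each contributing both sides.
- Two-sided 5% tests.
- w = correlation between the two sides of a patient at one visit: 0, 0.5 or 0.8.
- r = correlation between the baseline and three-month side differences: 0.3, 0.5 or 0.7, with lower values checked below.
- True effect 0.5 SD. The SD of a side difference is √(2(1−w)) score SDs. This equals 1 at w = 0.5, so the two scales coincide there.

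**Step 1: pairing.** The independent test uses a standard error of √(2/28) = 0.267 SD. At w = 0.5 the true standard error of the side difference is √(2 × 0.5/28) = 0.189 SD. The test is therefore too cautious: simulated null rejection is about 0.7% instead of 5%, and power on three-month scores is about 0.44. The paired t-test has noncentrality 0.5 × √28 = 2.646 on 27 df, giving power 0.723.

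**Step 2: baseline adjustment on top of pairing.** Relative to the paired three-month comparison, the variance factor is 1 − r² for adjustment with a known slope. Estimating the slope multiplies this by about 1 + 1/(n − 3) = 1 + 1/25 = 1.04. A change score has factor 2(1 − r). Each power uses noncentrality 2.646/√factor, with 26 df for adjustment and 27 df for the change score.

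| r | 1 − r² | × 1.04 | Noncentrality | Adjusted power | Change-score factor | Change-score power |
|---|---|---|---|---|---|---|
| 0 | 1.00 | 1.04 | 2.59 | 0.70 | 2.00 | 0.44 |
| 0.2 | 0.96 | 1.00 | 2.65 | 0.72 | 1.60 | 0.52 |
| 0.3 | 0.91 | 0.95 | 2.72 | 0.74 | 1.40 | 0.58 |
| 0.5 | 0.75 | 0.78 | 3.00 | 0.82 | 1.00 | 0.72 |
| 0.7 | 0.51 | 0.53 | 3.63 | 0.94 | 0.60 | 0.91 |

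With the slope treated as known (26 df) the adjusted powers would be 0.761, 0.837 and 0.946 at r = 0.3, 0.5 and 0.7. The table's figures are the realistic ones, and simulation (0.75, 0.82, 0.94) agrees with them.

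**Step 3: sensitivity to w.** Simulated power for an effect of 0.5 score SD:

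| w | Independent, three-month score | Paired | Paired and adjusted, r = 0.3 / 0.5 / 0.7 |
|---|---|---|---|
| 0 | 0.45–0.46 | 0.44 | 0.46 / 0.54 / 0.70 |
| 0.5 | 0.43–0.44 | 0.71–0.73 | 0.75 / 0.82 / 0.94 |
| 0.8 | 0.40–0.41 | 0.98 | 0.99 / 1.00 / 1.00 |

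**Step 4: chance baseline differences.** With 28 patients, the 95% limit of the chance difference between side means at baseline is 1.96 × √(2(1−w)/28). This is 0.52, 0.37 or 0.23 SD at w = 0, 0.5 or 0.8. If three-month scores are tested, a fraction r of that difference carries into the estimate. For r from 0.3 to 0.7 the carry-over at the limit is 0.16–0.37, 0.11–0.26 or 0.07–0.16 SD. If the stated total of 56 meant 56 patients, the limits would be 0.37, 0.26 or 0.17 SD.

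Averaged over randomisations the estimate is centred on the truth (simulated null mean about 0), and at w = 0.5 and 0.8 the planned test's null rejection rate is well below 5%.

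**The case against.** **A reader might infer that the plan discards the baseline scores and tests three-month values.** The text does not say so. A t-test can be run on change scores, and two other outcomes in this trial are changes from a starting state, so that reading is at least as natural. What stands is that the analysed value is not named. Neither reading is efficient: the three-month score leaves the baseline unused, and a change score is less precise than no adjustment when r is below 0.5. Both ignore pairing under the named test.

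**A reader might infer bias or a raised false-positive rate.** Side is allocated at random, so baseline differences are chance differences. The estimate is unbiased over randomisations, and positive correlation between sides makes the independent test conservative.

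**A reader might infer that the two teeth on a side enter as separate observations.** The plan gives no rule for combining them, but nothing says they are counted separately. That is a separate question.

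**The gain from baseline may be small.** This stands in part. Eligibility excludes poor oral hygiene and active periodontal disease, and patients are sent for periodontal checking and oral care before treatment. Low, coarse scores may leave little side difference at baseline and a low r. At r = 0.3 adjustment adds only about 2 points to a paired test. At w = 0.5, pairing brings more of the gain than baseline does for r of 0.3 to 0.5.

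**Conclusion.** The point holds as a loss of precision and an unspecified analysed value in two secondary outcomes. With 28 patients, w = 0.5 and a true effect of 0.5 SD of the side difference, pairing raises power from about 44% to 72%. Baseline adjustment then brings it to about 74%, 82% or 94% at r = 0.3, 0.5 or 0.7. Below r of about 0.2 adjustment adds nothing over pairing, and at r = 0 it costs about 2 points (0.723 to 0.705). If w is near 0, pairing itself brings nothing.

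The size rests on w, r and the effect, none of which the documents give. The direction does not: positive correlation between sides, which a split-mouth design presumes, makes the independent test inefficient, and the adjusted paired analysis does worse than the plain paired test only by a small margin at low r. The documents do not support a claim of bias or of an inflated error rate.

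**What to change.** For each index, pre-specify one score per side per visit: for example the canine, next to which the MOPs are placed, or the mean of the canine and second premolar. Averaging could dilute a local effect at the canine, so the choice should be fixed before analysis.

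Then regress each patient's three-month MOP-minus-control difference on the same patient's baseline MOP-minus-control difference, without centring the baseline difference. The intercept is the MOP effect at zero baseline side difference; report it with its 95% CI. Because the scores are coarse, add a Wilcoxon signed-rank test on the side difference in change as a check.

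This handles pairing and baseline in one model and settles which value is analysed. It needs no new data. The cost is two sentences in the Statistical analysis section, one degree of freedom, and at most about 2 points of power relative to a plain paired test if r proves very low.

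### Before-and-after root length of the same canine is compared with an independent-samples t-test; this ignores the pairing and, under most plausible SDs, loses most of the power to detect shortening of about 0.5 mm or less

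*Combined protocol and SAP*

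**What the plan says.** Secondary Outcomes describes root resorption as assessed "using the periapical radiographs of the canines before canine retraction and after three months". The quantity in millimetres "was measured by the difference between root length at baseline (R1) and after three months (R2"). R1 and R2 are therefore two lengths of the same tooth.

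The statistical analysis section plans two resorption analyses. The first is general: independent-samples t-tests are applied to the primary and "secondary outcomes to compare the difference between MOP and control sides". The second is specific to resorption: an "independent sample t-test was performed to compare the amount of root resorption before and after three months in MOP and control sides separately". No paired test is named anywhere in that section.

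The trial design section states: "This study was a split mouth randomized clinical trial with a 1:1 allocation". The sample size section gives 28 subjects per group, "yielding a total sample size estimate of 56 subjects", so the number of canines per side could be read as 28 or 56.

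**The concern.** An independent-samples t-test assumes two unrelated samples. Here the second sample is the first one measured again. Some patients have long canine roots and some short; that spread cancels when each tooth serves as its own control, but the independent test keeps it in the standard error. Whenever R1 and R2 are positively correlated, as repeat lengths of one tooth will be, the test rejects too rarely.

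The wording also does not fit the definition. Resorption is already R1 minus R2, so there is no amount of resorption before retraction. The only coherent reading is a comparison of R1 with R2, and that reading is used here.

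Resorption is a potential harm, so an insensitive test errs in the reassuring direction: real shortening could be reported as no significant resorption.

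**Working it through.** **The plan's own figure.** The only calculation in the plan is for a standardised effect of 0.8. A one-sided independent t-test at 0.05 needs 28 per group (power 90.5%), which reproduces 28 and 56. A two-sided test needs 34 per group; 28 gives 83.6%. The 0.8 is not tied to root length, so this says nothing about power for resorption.

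**Inputs.** From the documents: significance at p ≤ 0.05, and n = 28 or 56. Two-sided testing is assumed because sidedness is not stated. Also assumed, because the documents give neither: root-length SD of 1.0, 1.5 or 2.0 mm, and SD of the within-tooth change of 0.3, 0.5 or 0.8 mm. With equal SDs at both times the implied correlation is ρ = 1 − SD_change² / (2·SD²), from 0.68 to 0.99.

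**Mean shortening needed for p ≤ 0.05.**

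- Unpaired: t(0.975, 2n − 2) × SD × √(2/n).
  - n = 28: 2.005 × (0.267, 0.401, 0.535) = 0.54, 0.80, 1.07 mm.
  - n = 56: 1.982 × (0.189, 0.283, 0.378) = 0.37, 0.56, 0.75 mm.
- Paired: t(0.975, n − 1) × SD_change / √n.
  - n = 28: 2.052 × (0.057 to 0.151) = 0.12 to 0.31 mm.
  - n = 56: 2.004 × (0.040 to 0.107) = 0.08 to 0.21 mm.

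**Power.** Simulated with bivariate normal R1 and R2, 40,000 replicates per cell. Ranges run over SD_change 0.3 to 0.8 mm.

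| n | True shortening | Unpaired, SD 1.0 | Unpaired, SD 1.5 | Unpaired, SD 2.0 | Paired |
|---|---|---|---|---|---|
| 28 | 0.3 mm | up to 8% | up to 0.3% | about 0% | 48% to >99% |
| 28 | 0.5 mm | 37–43% | up to 5% | up to 0.3% | 89% to >99% |
| 28 | 1.0 mm | >99% | 87–95% | 35–38% | >99% |
| 56 | 0.3 mm | 8–26% | up to 1% | about 0% | 79% to >99% |
| 56 | 0.5 mm | 87–99% | 19–31% | up to 3% | >99% |
| 56 | 1.0 mm | >99% | >99% | 98% to >99% | >99% |

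**Under no change.** The unpaired test rejects in 0 to 0.1% of replicates instead of 5%; the paired test rejects in about 5%.

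**The planned between-side test.** If it uses R1 − R2, root-length variance is already removed, but the test still ignores that both canines belong to one patient. With n = 28:

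- Critical difference, unpaired: 2.005 × SD_change × √(2/28) = 0.16 to 0.43 mm.
- Critical difference, paired with left-right correlation r = 0.5: 2.052 × SD_change × √(2(1 − r)/28) = 0.12 to 0.31 mm.
- Power for a true 0.3 mm side difference with SD_change 0.8 mm: 21% unpaired and 48% paired at r = 0.5; 28% and 27% at r = 0.

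**The case against.** The case on the other side accepts that the named test is wrong and argues about its weight.

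- **The size of the loss is assumed.** This stands. Only the mismatch and its direction follow from the documents. With 56 patients and a root-length SD of 1.0 mm, power at 0.5 mm is 87–99% unpaired, so little is lost. If the SD of change is 1.0 mm, which is possible because the plan reports no reliability for root length, then at 28 patients, SD 1.0 mm and 0.5 mm shortening the figures are 43% against about 72%: a loss of about 40%, not most.
- **Pairing does not rescue very small effects.** This also stands. At 0.1 mm with 28 patients, paired power is only about 8% to 41%, so even a correct null result would need its confidence interval.
- **The within-side test is not the randomised comparison.** True. MOP against control is the randomised contrast and a test of it is planned, so the within-side error would not by itself hide an MOP effect. It inflates no false-positive rate and leaves the primary outcome untouched. The planned between-side test is, however, also unpaired, and the plan does not say whether it uses R1 − R2 or root length.
- **The between-side problem runs through the whole plan.** Fair. It is noted here only because it bears on resorption, and it adds no weight to the within-side point.

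None of this makes the independent test suitable for two readings of one tooth.

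**Conclusion.** The concern holds and should be fixed. That the test is wrong for the data, and conservative when R1 and R2 are positively correlated, needs no assumption about SDs. The size of the loss does: for root-length SDs of 1.0 to 2.0 mm and SDs of change of 0.3 to 0.8 mm, it is severe at 0.3 mm in every case. At 0.5 mm it is severe unless the SD is near 1.0 mm and there are 56 patients. At 1.0 mm it is small except with SD 2.0 mm and 28 patients. The consequence is confined to a secondary safety outcome: a non-significant before-and-after result within a side should not be read as absence of resorption.

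**What to change.** 1. Compute R1 − R2 for each tooth. Within each side, report mean shortening with its 95% CI and a paired (one-sample) t-test.
2. Replace the independent MOP-versus-control test for resorption with a paired t-test of R1 − R2 on the two sides of the same patient, with its 95% CI. State explicitly that R1 − R2 is the variable analysed, and base any statement about MOP-related resorption on this contrast.
3. Reword the within-side sentence so that it compares root length before and after, or tests mean R1 − R2 against zero, in line with the definition under Secondary Outcomes.

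The cost is a change of wording in the analysis section and a re-run on the same radiographic measurements.
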